9.3.3 Medical History, Medications, and Non-Drug Therapies

At screening, the subject's medical and surgical history will be described for the following body systems: eyes, ears, nose, and throat; respiratory; cardiovascular; gastrointestinal; musculoskeletal; neurological; endocrine; hematopoietic/lymphatic; dermatological; and genitourinary systems. Hemophilia history and treatment history will be captured, including start and end dates of past treatments where available.

All relevant medications and non-drug therapies received from enrollment until completion/termination will be recorded on the concomitant medications and non-drug therapies e-CRFs.

9.3.4 Physical Examinations

At interval visits, a physical examination (see also [Table 1](#)) will be performed. At screening, if an abnormal condition is detected, the condition will be described on the medical history e-CRF. At subsequent study visits, if a new abnormal or worsened abnormal pre-existing condition is detected, the condition will be described on the AE e-CRF. If the abnormal value was not deemed to be an AE because it was due to an error, due to a pre-existing disease (described in [Section 11.1.1.4](#)), not clinically significant, a symptom of a new/worsened condition already recorded as an AE, or due to another issue that must be specified, the investigator will record the justification on the source record.

9.3.5 Clinical Laboratory Parameters

The investigator's assessment of each laboratory value will be recorded on the eCRF. For each abnormal laboratory value, the investigator will determine whether the value is clinically significant or not. For clinically significant values, the investigator will indicate if the value constitutes a new AE (see definition in Section 11.1 , and record the sign, symptom, or medical diagnosis on the AE CRF), is a symptom or related to a previously recorded AE, is due to a preexisting disease (described in Section 11.1.1.4), or is due to another issue that will be specified. If the abnormal value was not clinically significant, the investigator will indicate the reason, ie because it is due to a preexisting disease, due to a lab error, or due to another issue that will be specified. However, additional tests and other evaluations required to establish the significance or etiology of an abnormal value, or to monitor the course of an AE should be obtained when clinically indicated. Any abnormal value that persists should be followed at the discretion of the investigator.

9.3.6 Vital Signs

Vital signs will include height (cm) and weight (kg). Height and weight will be collected, if available, at screening visit, each annual interval visit, and study completion/termination. For pediatric patients, percent of growth and height curves will be collected. Vital signs will be recorded on the CRF. For abnormal vital signs, the investigator will determine whether or not to report an AE (see definition in Section 11.1 and record the medical diagnosis (preferably), symptom, or sign on the AE CRF). Additional tests and other evaluations required to establish the significance or etiology of an abnormal value, or to monitor the course of an AE should be obtained when clinically indicated. Any abnormal value that persists should be followed at the discretion of the investigator.

9.3.7 Subject Completion/Discontinuation

A subject is considered to have completed the study when he/she ceases active participation in the study because the subject has, or is presumed to have, completed the study according to the protocol.

Reasons for completion/discontinuation will be reported on the Completion/Discontinuation CRF, including: completed, screen failure, discontinuation due to an AE, discontinuation by subject (eg, lost to follow-up, dropout), study terminated by the MAH, or other (reason to be specified by the investigator). Regardless of the reason, all data available for the subject up to the time of completion/discontinuation should be recorded on the appropriate CRF and will be used in the analysis and included in the study report.

In the event of subject discontinuation due to an AE, clinical and/or laboratory investigations performed as part of the evaluation of the event will be reported to the MAH. Details of the outcome may be reported to the appropriate regulatory authorities by the responsible party.

9.4 Data Sources

9.4.1 Source Data

Source data are defined as all information in original records and certified copies of original records of clinical findings, observations, or other activities in a trial that are necessary for the reconstruction and evaluation of the trial. Source data are contained in source documents (original records or certified copies), which may be in paper and/or electronic format. Source data for this study comprise the following: hospital records, medical records, clinical and office charts, laboratory notes, questionnaires, subject diaries or evaluation checklists, outcomes reported by subjects, recorded data from automated instruments, copies or transcriptions certified after verification as being accurate copies, microfiches, photographic negatives, microfilm or magnetic media, x-rays, subject files, and records kept at the pharmacy, at the laboratories, and at medico-technical departments involved in the study.

For additional information on study documentation and CRFs see Section 9.6.1. The use of subject diaries is described in Section 9.4.2.

Data will be prospectively collected at the centers and recorded onto e-CRFs from hospital medical records and the subject diaries (paper or electronic) documented by the patient (see Section 9.4.2).

9.4.2 Subject Diary

It is considered standard practice for subjects with hemophilia to maintain a diary which captures treatments and disease-related data.

Both paper and electronic subject diaries will be used in this study. Diaries will be offered to each subject at the screening visit and at annual visits to record the following information:

- Number of RIXUBIS units required for bleed resolution
- Number of RIXUBIS infusions required for bleed resolution
- Bleeding episodes
- Effectiveness assessment for the treatment of each bleed

- Number of days in which subjects cannot follow normal daily routine (e. g. school, work) due to bleeding episodes or their treatment
- Acute pain assessment using Numeric Rating Scale (NRS) or Pediatric Wong Baker Face Scale

Completion of the subject diary is a voluntary effort by the individual subject or subject's legally authorized representative. If used, the diary will remain with the subject for the duration of the study. Untoward events recorded in the diary will be reported as AEs according to the investigator's discretion and clinical judgment.

Subject entries in the diaries will serve as source records. In the case of eDiaries, the investigator has access to the database holding the subject diary data. After study closure, the investigator will receive the eDiary records for their subjects, including audit trail records, in PDF format. The data will be transmitted to the CRF by a validated transfer.

In the case of paper diaries, entries in the subject diary will be transferred into the appropriate collection device. Any entry in the collection device that does not correspond with an entry in the subject diary will be explained by the investigator in source documentation.

9.5 Study Size

As no hypothesis testing or interval estimation will be applied, the sample size for the study is not based on statistical considerations. The sample size of approximately 80 evaluable subjects was selected as a reasonable number for a non-interventional study to recruit over the enrolment period planned for the study.

9.6 Data Management

9.6.1 Data Collection Methods

The investigator will maintain complete and accurate paper format study documentation in a separate file. Study documentation may include information defined as "source data" (see Section 9.4.1) records detailing the progress of the study for each subject, signed informed consent forms, correspondence with the EC and the study monitor/MAH, enrollment and screening information, CRFs, SAE reports (SAERs), laboratory reports (if applicable), subject diaries (if used), and data clarifications requested by the MAH.

The investigator will comply with the procedures for data recording and reporting. Any corrections to paper source documentation must be performed as follows: 1) the first entry will be crossed out entirely, remaining legible; and 2) each correction must be dated and initialed by the person correcting the entry; the use of correction fluid and erasing are prohibited.

The investigator is responsible for the procurement of data and for the quality of data recorded on the CRFs. CRFs will be provided in electronic form and all data should be entered within 5 days of becoming available.

Only authorized study site personnel will record or change data on the CRFs. If data is not entered on the CRFs during the study visit, the data will be recorded on paper; and this documentation will be considered source documentation. Changes to a CRF will require documentation of the reason for each change. An identical (electronic) version of the complete set of CRFs for each subject will remain in the investigator file at the study site.

The handling of data by the MAH, including data quality assurance, will comply with regulatory guidelines and the standard operating procedures of the MAH. Data management and control processes specific to the study will be described in the data management plan (see Section 14.1).

9.6.2 Laboratory and Reader Standardization

No central laboratories will be used, and no inter-laboratory standardization methods and reader standardization methods for laboratory tests will be carried out. Each local laboratory will provide normal value ranges.

9.6.3 Software

All data processing, summarization and analyses will be performed with the SAS[®], using the most current accessible version of SAS software.

9.7 Data Analysis

9.7.1 Datasets and Analysis Cohorts

The effectiveness analysis will be carried out on the primary and secondary endpoints of the study for the following treatment regimens:

- Standard prophylaxis
- On-demand treatment
- Episodic prophylaxis
- ITI

Effectiveness of switch from on-demand to prophylaxis dataset (ESODTP)

Evaluation of effectiveness (ABR, AJBR) after switch from on-demand regimen to prophylaxis in moderate moderately severe and severe hemophilia B patients.

Safety Analysis Set (SAS)

The SAS will consist of data for all subjects who were enrolled, met all inclusion and none of the exclusion criteria, and received at least 1 infusion of FIX (RIXUBIS). If 2 or more AEs are reported together as a unit, the individual Medical Dictionary for Regulatory Activities (MedDRA) preferred terms will be counted as separate events.

Effectiveness Full Analysis Set (EFAS)

The EFAS will consist of data from all subjects who were enrolled, met all inclusion and none of the exclusion criteria. This dataset will be used for the primary effectiveness analysis for the comparison of annualized bleeding rates (ABR, AJBR) between each independent treatment regimen (i.e., prophylaxis, on-demand).

Calculation of Annualized Bleeding Rates (ABR) and monthly Bleeding Rate (MBR)

The ABR will be calculated as follows: $(\text{total number of bleeding episodes} \div \text{observed treatment period in days}) * 365.25$. The monthly bleeding rates (MBR) will be calculated as follows: $(\text{total number of bleeding episodes} \div \text{observed treatment period in days}) * 30.5$. The treatment period for surgeries will be excluded from the bleed rate calculation.

Bleeding occurring prior to the first prophylactic infusion will not be included in the estimation of bleeding rate. The observation period for the on-demand regimen will commence on the day of enrollment (met all inclusion and none of the exclusion criteria); the period for prophylaxis will commence at the first prophylactic infusion once enrolled (met all inclusion and none of the exclusion criteria).

Minimal Observed Treatment Period to Estimate ABR

For enrolled subjects that have met all inclusion and none of the exclusion criteria, subjects who have at least 1 assessment [defined as having a minimum of 3-month (≥ 90 days) observational period on regimen] but do not complete the full study period of four years, the ABR will be estimated from the interval assessments. For subjects who do not have at least 1 interval assessment, the median rate observed for the assigned regimen will be substituted.

Health Related Quality of Life Analysis Set (HRQoLAS)

The HRQoLAS will consist of all subjects who have been enrolled and met all inclusion and none of the exclusion criteria and who have provided any available assessments at any available study visit.

Pharmacoeconomics Analysis Set (PEAS)

The PEAS will consist of all the subjects that have been enrolled, met all inclusion and none of the exclusion criteria and have provided any available assessments at any available study visit.

Joint Health/Function Analysis Set (JHFAS)

The JHFAS will consist of all subjects who have been enrolled, met all inclusion and none of the exclusion criteria and have provided any available assessments at any available study visit.

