RIXUBIS was investigated for prophylactic use in pediatric PTPs aged <12 years with severe (FIX level < 1%) or moderately severe (FIX level 1-2%) hemophilia B. The purpose of this prospective clinical trial was to assess the safety, hemostatic efficacy, and PK profile of RIXUBIS which was administered as prophylaxis twice a week over 6 months, and on-demand for treatment of bleeds. Safety was assessed by the occurrence of related AEs, thrombotic events and immunologic assessments. Efficacy was evaluated by ABR, and by treatment response rating (excellent, good, fair, none). PK was assessed over 72 hours.

None of the 23 treated subjects experienced an SAE or AE related to treatment. There were no thrombotic events, and no inhibitory or specific binding antibodies against FIX, rFurin or CHO protein. Twenty-six bleeds (19 non-joint vs. 7 joint bleeds) occurred, of which 23 were injury-related (mean ABR 2.7 ± 3.14 , median 2.0). Twenty subjects (87%) did not experience any bleeds of spontaneous etiology. Hemostatic efficacy of RIXUBIS was excellent or good for >96% of bleeds (100% of minor, 88.9% of moderate, and 100% of major bleeds); the majority (88.5%) resolved after 1-2 infusions. The PK analysis revealed that the incremental recovery (IR) 30 minutes after infusion was consistent over time. IR was associated with age, increasing IR was observed with increasing age (mean IR of all subjects (n=23): 0.665 ± 0.1632 (median 0.685); subjects <6 years (n=11): mean IR 0.586 ± 0.1320 (median 0.591); and in subjects between 6 and 12 years mean IR was 0.731 ± 0.1615 (median 0.714). Longer $T_{1/2}$ and lower IR were observed in younger children (<6 years) compared to the older age group. In summary, RIXUBIS was efficacious in preventing and controlling bleeds, and was safe in pediatric patients aged <12 years with hemophilia B ^{9;10;11}.

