9.2.3.2 Exclusion Criteria

Subjects who meet **ANY** of the following criteria are not eligible for this study:

- Known hypersensitivity or presence of any contraindication to rFIX
- Disseminated intravascular coagulation (DIC)
- Acute thrombosis or embolism (including myocardial infarction)
- Other severe concomitant clinically relevant conditions or bleeding disorders that in the investigator's opinion precludes the inclusion of the patient.

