9.2.4 Informed Consent and Enrollment

Any patient who directly, or indirectly through a legally authorized representative, provides informed consent (ie, signs and dates the informed consent form (ICF) or assent form, if applicable) is considered to be enrolled in the study.

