9.3.2.2 Safety and Immunogenicity

- Incidence of inhibitors in PTPs with history of inhibitors and with FIX <1%, ≤2% and >2-5%
- Incidence of inhibitors in PTPs without history of inhibitors and with FIX <1%, ≤2% and >2-5%
- Incidence of inhibitors in previously untreated patients (PUPs) with FIX <1% and ≤2% and >2-5%
- Treatment regime after an inhibitor has occurred in PUPs and PTPs
- Incidence and severity of SAE and NSAE
- Incidence and severity of therapy-related SAE and NSAE
- Incidence of life-threatening bleeding episodes
- Incidence of thromboembolic events.

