11. MANAGEMENT AND REPORTING OF ADVERSE EVENTS/ADVERSE REACTIONS

11.1 Adverse Events

Each AE from the point of enrolment until study completion will be described on the AE e-CRF using the medical diagnosis (preferred), or, if no diagnosis could be established at the time of reporting the AE, a symptom or sign, in standard medical terminology in order to avoid the use of vague, ambiguous, or colloquial expressions (see definitions in Section 11.1.1). Each AE will be evaluated by the investigator for:

- Seriousness as defined in Section 11.1.1.1
- Severity as defined in Section 11.1.2.1
- Causal relationship to medicinal product exposure as defined in Section 11.1.2.2

For each AE, the outcome (ie, recovering/resolving, recovered/resolved, recovered/resolved with sequelae, not recovered/not resolved, fatal, unknown) and action taken (ie, dose increased, dose not changed, dose reduced, drug interrupted, drug withdrawn, not applicable, or unknown) will also be recorded on the AE e-CRF. Recovering/resolving AEs will be followed until resolution, medically stabilized, or 30 days after the study completion/termination visit, whichever comes first.

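### The Safety Analysis Set drops RIXUBIS-treated subjects later found ineligible, contrary to the protocol's own data-use rule; secondarily, the FIX categories for inhibitor incidence overlap

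*Protocol*

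**What the plan says.** Section 9.7.1 defines the Safety Analysis Set as subjects "who were enrolled, met all inclusion and none of the exclusion criteria, and received at least 1 infusion of FIX (RIXUBIS"). Eligibility is thus a condition in addition to treatment.

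Three other sections bear on this:

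- Section 9.2.4: anyone who gives consent "is considered to be enrolled in the study". Eligibility plays no part.
- Section 11.1: "Each AE from the point of enrolment until study completion will be described on the AE e-CRF". Recording starts at consent.
- Section 9.3.7 lists screen failure among the reasons for leaving the study. It then says that, whatever the reason, all available data "will be used in the analysis and included in the study report".

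The exclusion criteria in 9.2.3.2 cover known hypersensitivity, DIC, "Acute thrombosis or embolism (including myocardial infarction") and an investigator-judgement item. The safety variables in 9.3.2.2 include "Incidence of thromboembolic events".

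For inhibitors, 9.3.2.2 lists, for example, "Incidence of inhibitors in PTPs without history of inhibitors and with FIX <1%, ≤2% and >2-5"%. The same three FIX categories are used for previously treated patients with an inhibitor history and for previously untreated patients. In section 7.2, the paragraph on the paediatric study pairs severe disease (below 1%) with "moderately severe (FIX level 1-2"%).

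**The concern.** A safety set normally follows exposure: whoever received the product is counted. Here a treated subject is removed if a criterion turns out not to have been met. Such subjects are plausible in this design, because RIXUBIS must already be prescribed before participation (9.1) and exposure days to RIXUBIS are recorded at screening (9.2.6). A subject who fails a criterion may therefore already be on the product. Some of the exclusions relate to events the study has to describe, so the removal cannot be presumed neutral. The sections also give conflicting instructions on whether these data are analysed.

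The inhibitor categories raise a smaller issue. Anyone below 1% is also at or below 2%, so the first category lies inside the second, and no row shows 1 to 2% by itself.

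**Working it through.** The protocol derives no figure on this point. The sample size of about 80 is a feasibility number (9.5), so there is nothing to reproduce. The check is a comparison of definitions, followed by illustrations on stated assumptions.

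**1. Who is dropped**

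- Treated group: enrolled and infused.
- Safety Analysis Set: enrolled, infused and eligible.
- Difference: enrolled, infused and ineligible, numbering k.

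Because 9.2.4 does not tie enrolment to eligibility, k can exceed zero. By 11.1 and 9.3.7 the events of these k subjects are collected and are to be analysed; by 9.7.1 they fall outside the set.

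**2. Size**

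Take 80 as the number infused. The protocol does not give k, so k = 2, 4 and 8 are assumed. Let x events fall among the dropped subjects and none among the rest. Intervals are exact (Clopper-Pearson) 95%.

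| k | Safety set as written | All treated, x = 1 | All treated, x = 2 |
|---|---|---|---|
| 2 | 0/78 (0 to 4.62%) | 1/80 = 1.25% (0.03 to 6.77%) | 2/80 = 2.50% (0.30 to 8.74%) |
| 4 | 0/76 (0 to 4.74%) | same | same |
| 8 | 0/72 (0 to 4.99%) | same | same |

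**3. Direction**

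With e events among the eligible, the set reports e/(80 − k), while the treated rate is (e + x)/80. The treated rate is a weighted average of e/(80 − k) and x/k. The reported rate is therefore too low only if x/k exceeds e/(80 − k). If the dropped subjects have no event and there is one among the rest, with k = 4, the set reports 1/76 = 1.32% against 1/80 = 1.25%, which is slightly too high.

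**4. FIX categories**

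Let a, b and c be the numbers with FIX below 1%, 1 to 2%, and above 2 to 5%. The rows as written hold a, a + b and c subjects. Their sum is 80 + a, so the excess is the number of severe subjects. Assumed mixes:

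| a / b / c | Rows as written | Sum |
|---|---|---|
| 60 / 10 / 10 | 60, 70, 10 | 140 |
| 40 / 20 / 20 | 40, 60, 20 | 120 |
| 20 / 30 / 30 | 20, 50, 30 | 100 |

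Section 7.2 gives an inhibitor risk of 1 to 5% for severe haemophilia B. Applied to 40 severe subjects only, this is 40 × 0.01 = 0.4 to 40 × 0.05 = 2 expected cases. At 5%, and with no case in the 1 to 2% group, the middle row reads 2/60 = 3.3%. Subtracting the first row gives 0 cases in 60 − 40 = 20 subjects. The 1 to 2% result is recoverable, but the table does not display it.

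**The case against.** **Safety set.** A reader might infer that the safety rates are biased downward. The documents do not support that. Subjects can also fail because their FIX level is above 5% (9.2.3.1) or on the investigator's judgement (9.2.3.2), and neither implies an obvious excess of thrombotic or allergic events. A thrombosis present at entry is a preexisting disease and is not an adverse event unless it worsens (11.1.1.4). Eligibility is checked at screening, so k may be small or zero. Nor are the events lost to the sponsor: serious events are reported within 24 hours and all events are recorded from enrolment. All this stands. What it leaves untouched is that the set as defined omits treated subjects whose data 9.3.7 says will be analysed.

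**FIX categories.** It is tempting to say that severe subjects are double counted and that incidence in moderately severe subjects cannot be shown. Neither holds. Nothing in the protocol adds the rows, no case is counted twice within a row, and each row is a valid proportion if the middle one is cumulative. In its account of the adult phase I/III study, section 7.2 also uses up to 2% as the label for moderately severe disease, so the intention may have been disjoint. What stands is an ambiguity of labelling.

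**Existing inhibitors.** No exclusion names a current inhibitor, and immune tolerance induction is an analysed regimen, so a reader might infer that the incidence figures generally mix existing with new inhibitors. The split by inhibitor history in 9.3.2.2 largely prevents this: a previously treated patient known to be positive at entry has a history and stays out of the row without history. Only the row with history needs a distinction.

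**Requiring a later test.** Limiting the denominator to subjects with a later inhibitor test would bring its own problem. Testing follows routine practice and interim tests are as needed (Table 2), so the restriction could select subjects tested on suspicion.

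**Conclusion.** The main point holds as a defect of definition. Followed as written, 9.7.1 removes enrolled, infused subjects from the safety set if they prove ineligible, in conflict with 9.3.7 and out of step with 11.1. This is fixed in the protocol itself and is not a detail awaiting the analysis plan. The effect is unknown and may be nil. It matters because, at about 80 subjects, a single dropped case can be the difference between a reported event and none, as 1/80 against 0/76 shows under the assumption of four ineligible treated subjects, one of them with the event.

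The overlap in the FIX categories is real but secondary: a matter of clear presentation, not of invalid rates. The point on existing inhibitors is confined to the row with an inhibitor history.

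**What to change.** 1. In 9.7.1, define the Safety Analysis Set as all enrolled subjects with at least one RIXUBIS infusion, regardless of eligibility. Flag ineligible subjects so that they can be identified in the safety tables.
2. Align 9.3.7 with this, so that both sections say the same about infused subjects recorded as screen failures.
3. In 9.3.2.2, use disjoint categories (below 1%, 1 to 2%, above 2 to 5%) for both groups of previously treated patients and for previously untreated patients, or label the category up to 2% as cumulative.
4. In the row with an inhibitor history, list subjects positive at screening separately from new or recurrent cases. Do not require a later inhibitor test for the main denominator; if such a restriction is wanted, report it as a sensitivity analysis.

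The cost is wording. Eligibility, infusions, adverse events and baseline FIX levels are already collected, as are screening inhibitor results where routine practice provides them. Safety counts may change slightly, in either direction.

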14.3 Additional Information

List of Definitions

Important terms	Definitions
Chronic pain:	Continuous and/or intermittent pain, related to the pathophysiology of hemophilia, requiring intervention (pharmacological or non-pharmacological treatment), and in which the cause of pain cannot be readily removed, occurring more than once a week and lasting 3 months or more”
Episodic prophylaxis	Episodic prophylaxis lasting no more than 3 months.
High responding inhibitors:	“inhibitors with peak activity >5 Bethesda Units (BU/mL) associated with anamnesis following replacement of the missing clotting factor.” and this level >5 BU/mL “is maintained at any time”.
On-demand treatment	Treatment of acute bleeds with any factor concentrates with the goal to resolve bleeds
Prophylaxis	Regular administration of factor concentrates with the goal to prevent bleeds. For analysis purposes, in this protocol, Hemophilia B prophylaxis is defined as follows: at least one administration per week. Long term prophylaxis lasting for one year or more. Short term prophylaxis lasting for more than 3 months.
Target Joint	A target joint is defined as a joint in which at least 3 or more spontaneous bleeds into a single joint within a consecutive 6 month period. Where there have been ≤ 2 bleeds into the joint within a consecutive 12 month period the joint is no longer considered a target joint (Blanchette et al 2014) ¹⁹

APPENDIX 1

Assessment of effectiveness

Total number (%) of treated bleeds and their corresponding hemostatic effectiveness ratings using an “excellent-to-poor” 4-point Likert scale by the subjects/care-giver (subjects <12 years: care-giver, subjects ≥ 12 years: self assessment) for treatments given at home, or by the investigator for treatments given in the hospital/clinic.

Excellent	Full relief of pain and cessation of objective signs of bleeding (e.g., swelling, tenderness, and decreased range of motion in the case of musculoskeletal hemorrhage) within approximately 6 hours to 12 hours and after 1 or 2 infusions. No additional infusion is required for the control of bleeding. Any additional infusion for treatment of bleeding will preclude this rating. Administration of further infusions to maintain hemostasis would not affect this scoring.

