Good	Definite pain relief and/or improvement in signs of bleeding within approximately 6 hours to 24 hours requiring more than 2 infusions for complete resolution. Administration of further infusions to maintain hemostasis would not affect this scoring.
Fair	Probable and/or slight relief of pain and slight improvement in signs of bleeding within approximately 6 hours to 24 hours. Requires multiple infusions for complete resolution.
Poor	No improvement of signs or symptoms or conditions worsen.

For prevention of bleeding episodes:

Annualized (ABR) and/or monthly bleeding rate (MBR), all bleeds, will be calculated as appropriate, based on the following formula: $ABR = (\text{number of bleeds/observational period days}) \times 365.25$; $MBR = (\text{number of bleeds/observational period} - \text{days}) \times 30.44$

- ✓ ABR and/or MBR will be calculated as appropriate, in all joint bleeding events
- ✓ Assessment of hemostatic effectiveness
 - The effectiveness will be assessed by a “excellent-to-poor” 4-point Likert scale by the subjects/care-giver (subjects <12 years: care-giver, subjects ≥ 12 years: self assessment) at the end of each prophylaxis period (if possible rated within 24 hours from the end of the prophylactic treatment) or on an annual basis, whichever occurs first.

Table 4 Overall Effectiveness Assessment for Prophylaxis Therapy	
Excellent	Definitely low bleeding rate with improvement in daily activities and quality of life. Very satisfied with the treatment and worth being continued-
Good	Relatively low bleeding rate with some improvement in daily activities and quality of life. Satisfied with the treatment and worth being continued-
Fair	Relative increase in breakthrough bleeding episodes with only partial benefit in terms of activity level and quality of life. Partially satisfied with the treatment. Not sure if it is worth continuing treatment
Poor	Frequent breakthrough bleeding episodes interfering with activity level and quality of life. Not satisfied with the treatment.

APPENDIX 2

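### Section 9.7.1 drops bleeds before the first prophylactic infusion from every bleeding rate but counts on-demand days from enrollment, so subjects who switch get an on-demand ABR of 0; the monthly rate also has two factors.

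*Protocol*

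**What the plan says.** Section 9.7.1 defines the ABR as bleeds divided by the days of the observed treatment period, times 365.25 ("The ABR will be calculated as follows"). It then sets three rules on what is counted:

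- Numerator: "Bleeding occurring prior to the first prophylactic infusion will not be included in the estimation of bleeding rate". No regimen is named.
- On-demand days: "The observation period for the on-demand regimen will commence on the day of enrollment".
- Prophylaxis days: "the period for prophylaxis will commence at the first prophylactic infusion once enrolled".

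The only time that it removes is that around surgery. It gives no end date for a regimen period.

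The same section sets up a dataset for subjects who change from on-demand to prophylaxis, and describes the comparison of bleeding rates between regimens in the full analysis set as the primary effectiveness analysis. Section 9.7.3.2 names the ABR under prophylaxis as the primary endpoint and asks for separate ABRs for standard prophylaxis, on-demand, episodic prophylaxis and immune tolerance induction (ITI), each with at least 90 days observed. Section 9.7.3.4.1 again asks for an on-demand ABR.

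The monthly bleeding rate (MBR) is defined twice. In section 9.7.1 ("The monthly bleeding rates (MBR) will be calculated as follows") the daily rate is multiplied by 30.5. In Appendix 1 ("Annualized (ABR) and/or monthly bleeding rate (MBR), all bleeds, will be calculated as appropriate, based on the following formula") it is multiplied by 30.44.

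**The concern.** A rate is meaningful only if its bleeds and its days come from the same time. For a subject who starts on-demand and later takes up prophylaxis, the exclusion sentence removes every bleed of the on-demand stretch, while the on-demand period still starts at enrollment. The result is days without bleeds.

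The protocol expects such subjects, since it plans a dataset for them. Their zero rates would enter the on-demand summary and pull it down. Prophylaxis would then look less effective relative to on-demand than it is, by an amount set by how many subjects switch and not by bleeding.

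The two MBR factors are a plain contradiction, though a small one.

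**Working it through.** **Inputs.** ABR formula, exclusion and start rules: section 9.7.1. Background ABRs: section 7.2, which reports 4.2 on prophylaxis and 20.0 in a historical on-demand group from an earlier trial. Follow-up: 4 years (section 9.1). The switch time and the share of switchers are assumptions; the protocol gives neither.

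**Check of the inputs.** 1 − 4.2/20.0 = 0.79, which agrees with the 79% reduction stated in section 7.2.

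**One subject, 12 months on-demand and then 36 months on prophylaxis.** Expected bleeds are 20 in 365.25 days on-demand and 4.2 × 3 = 12.6 in 1,095.75 days on prophylaxis.

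| Rule | On-demand ABR | Prophylaxis ABR |
|---|---|---|
| Bleeds and days over the same interval | 20/365.25 × 365.25 = 20.0 | 12.6/1,095.75 × 365.25 = 4.2 |
| Section 9.7.1 as written | 0/365.25 × 365.25 = 0 | 12.6/1,095.75 × 365.25 = 4.2 |

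The on-demand result is 0 whatever the switch time. The prophylaxis result does not change, because its bleeds and days both start at the first prophylactic infusion.

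**Group mean.** With a share s of on-demand subjects who later switch, and each subject's ABR weighted equally, the mean on-demand ABR is 20.0 × (1 − s). The apparent reduction is 1 − 4.2/[20.0 × (1 − s)].

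| s (assumed) | Mean on-demand ABR | Apparent reduction |
|---|---|---|
| 0 | 20.0 | 79% |
| 10% | 18.0 | 1 − 4.2/18 = 77% |
| 25% | 15.0 | 1 − 4.2/15 = 72% |
| 50% | 10.0 | 1 − 4.2/10 = 58% |

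**MBR factor.** 365.25/12 = 30.4375, which rounds to 30.44. The ratio 30.5/30.44 is 1.0020, a difference of 0.2%. Only the Appendix 1 factor is consistent with the 365.25 used for the ABR.

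**The case against.** The best defence is that the exclusion sentence was meant only as the numerator counterpart of the prophylaxis start rule that follows it. A subject who is always on-demand has no first prophylactic infusion, so a rule for all rates makes little sense for that subject, and the protocol plainly wants an on-demand ABR. This is probably the intention. But the text does not say so, and for a switcher the literal rule can be applied without difficulty and gives a wrong answer.

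Several stronger conclusions are tempting, and the protocol does not support them.

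- *The primary prophylaxis ABR is biased.* It is not, since its start points match. It would fall, for example to 12.6/1,461 × 365.25 = 3.15 in the subject above, only if on-demand days were put into the prophylaxis denominator. Section 9.7.1 does not do that.
- *The switch analysis has no usable earlier rate.* The switch dataset is defined by bleeding after the switch, and section 9.2.6 collects bleeding over the last 12 months at screening. That rate is not named as the comparator, but it exists.
- *Undocumented diary days count as bleed-free.* It is true that "Completion of the subject diary is a voluntary effort by the individual subject". But no sentence counts such days as bleed-free, the denominator is described as observed time without a definition, and visits and medical records are further sources of bleeds.
- *Bleeding on other products is credited to RIXUBIS.* The glossary does define on-demand as "Treatment of acute bleeds with any factor concentrates with the goal to resolve bleeds", but the objective and the inclusion criteria concern RIXUBIS, and no sentence keeps or removes time on another product. In such time bleeds and days would stay or go together, so the question is one of attribution and not of mismatch.

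The last two depend on how the observed treatment period is defined, which a statistical analysis plan commonly settles. They are not shown errors.

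**Conclusion.** The point holds for the on-demand rate. As written, section 9.7.1 gives an on-demand ABR of 0 to any subject who later starts prophylaxis. It thereby biases the on-demand ABR downward, and with it the prophylaxis versus on-demand comparison. The prophylaxis ABR named as the primary endpoint in section 9.7.3.2 is unaffected.

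The size depends on the share of switchers among on-demand subjects with enough time for an ABR. The range above rests on assumed shares of 10% to 50%, on background rates from an earlier trial, and on the literal reading. If the analysis follows the likely intention, the bias disappears.

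The MBR factors contradict each other with certainty, but the effect is 0.2%.

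**What to change.** Replace the exclusion sentence in section 9.7.1 with a rule that covers all four regimens (prophylaxis, on-demand, episodic prophylaxis, ITI):

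1. For each regimen, bleeds and days are counted over the same interval or intervals on that regimen. Each interval runs from the start of the regimen, or from enrollment if later, to the day before a change of regimen or to the end of observation.
2. The exclusion of time before the first prophylactic infusion applies only to the prophylaxis rate, and to both its bleeds and its days.

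The rule should not simply end on-demand time at the first prophylactic infusion. That would leave a subject who moves from prophylaxis to on-demand without an on-demand rate, and would not deal with episodic prophylaxis or ITI.

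Use 365.25/12 (30.44) for the MBR in both section 9.7.1 and Appendix 1.

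As a suggestion only, the definition of the observed treatment period could also state how time without bleed records and time off RIXUBIS are handled.

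The cost of the two corrections is wording. Dates of regimen change are already among the data listed in section 9.2.6.
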